#### **7.4 Determining Patients Eligible for EIMG Referral**

During the data extraction process, a list of patients that were eligible for an EIMG referral (regardless of whether they received a referral or not) will be extracted from the Prisma Health EHR. The research study team will retrospectively identify patients that could have received an EIMG referral based on a list of pre-determined ICD-10 codes.

*Inclusion Criteria.* The study team will develop a list of ICD-10 codes (based off the criteria presented in section 7.2.1.) to identify all potentially eligible patients that could have received an EIMG referral. The ICD-10 codes were selected a-priori by the study team based on the priority health conditions identified by Prisma Health leadership in partnership with the EIMG Advisory Board. These conditions include patients that are physically inactive and/or who have obesity, diabetes, hypertension, or dyslipidemia. The list of ICD-10 codes was selected by the research team and verified by: a) the EIMG Advisory Board, and b) Prisma Health primary care clinicians.

*Exclusion Criteria.* During phase I and II of the study (prior to any extraction of patient data from the Prisma Health EHR), the research team will engage in a process to develop a list of exclusionary criteria. Patients seeking medical assistance with any of these criteria would be deemed ineligible to receive an EIMG referral and will be removed from the denominator of our implementation, reach, and effectiveness analyses. To develop the list of exclusionary criteria, we will engage in a three-step process. First, we will identify published guidelines and existing tools (e.g., PAR-Q+) that list health conditions that are contraindications for physical activity. Second, we will seek the opinions of 8-12 primary care physicians to identify conditions for which they would not refer their patients to a physical activity program. Combining these findings, we will develop a list of ICD-10 codes that will serve as exclusionary criteria for which exercise training is either inappropriate or contraindicated.

*The final list of patients deemed eligible for a referral (inclusion criteria – exclusion criteria) will serve as the ‘denominator’ in our Reach calculations (see 14.1 and 14.2).*

	Definition	Description
Numerator	# of eligible patients that receive an EIMG referral	
 
• Determined through a real time patient workflow process in Prisma Health primary care clinics participating in the study
 

Denominator	# of patients that were eligible to have received an EIMG referral	
 
• Retrospectively pulled from the Prisma Health EHR
 
• Determine number of eligible patients based in ICD-10 inclusion criteria (Appendix A)
 
• Remove ineligible patients based off ICD-10 exclusionary criteria
 

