### 4.2 Patient Eligibility

Patients are eligible to participate in EIMG if they are between the ages of 18-80, physically inactive (<150 minutes per week of moderate intensity aerobic activity) and with or without a chronic condition (i.e., overweight/obese, hypertension, type 2 diabetes) that is positively impacted by PA. Patients with uncontrolled hypertension or diabetes, and those at increased fall risk are ineligible to participate in EIMG until symptoms are controlled and physician approval is provided.

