### 4.3 EIMG Clinic Workflow

The EIMG Clinician Decision Modules are incorporated into the EHR as part of clinical workflow. The three Decision Modules include: 1) PA assessment, 2) PA prescription (through patient order sets), and 3) referral to a community PA facility.

**Module 1: PA Assessment.** Front office or nursing staff capture the patient's current PA behavior via the PAVS programmed into the EHR. The PAVS consists of two questions (“how many minutes per day do you exercise?” and “how many days per week?”) to determine if the patient is meeting national PA guidelines of 150 minutes of moderate intensity aerobic activity a week. The PAVS identifies ‘eligible’ patients, provides a best practice alert (BPA) through the EHR stating that the patient may qualify for EIMG, and prompts providers to discuss lifestyle behavior change.

**Module 2: PA Prescription.** The healthcare provider informs eligible patients about the EIMG program, reviews risks, and provides basic PA and health education by providing them with *EIM Rx for Health* handouts for exercising with chronic disease (e.g., obesity, diabetes, hypertension, peripheral artery disease), developed by experts in the field. The healthcare provider then electronically starts an ‘EIMG Order Set’ leading to the patient referral.

**Module 3: Patient Referral.** Through a series of EHR prompts confirming patient eligibility, the healthcare provider sends a referral to the *EIMG Referral Team*. All aspects of the EHR referral process are electronic, except a paper version of the EIMG Consent to Treat and the Release of Information that the patient must sign (either while in the clinic room or at the checkout counter) in order to continue.

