### 7.2 Prisma Health – Patient Eligibility

Adult patients (≥18 years of age) will be deemed eligible for the study through two different approaches. First, patient eligibility to receive an EIMG referral is determined in real time through a series of steps that are integrated within the patient workflow process in the Prisma Health primary care clinics. Patients that receive an EIMG referral will have the opportunity to enroll in the community-based PA programs and will be considered as the numerator in our ‘reach’ calculations. Second, all patients that were eligible for an EIMG referral (whether they received one or not) at participating clinics will be identified through a retrospective data extraction process from the Prisma Health EHR that will occur at the end of the study period (end of month 8). These broader sample of patients that were eligible for an EIMG referral will be considered as the denominator in our ‘reach’ calculations.

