### 7.3 Patient Eligibility – Participating in the PA Program

Healthcare providers at participating Prisma Health primary care clinics that adopt EIMG will have the ability to identify eligible patients and provide them with an EIMG referral during the patient visit through a process embedded in the patient care workflow at each clinic.

The first step in determining patient eligibility to receive an EIMG referral will involve identifying potentially eligible patients that would benefit the most from participating in an exercise training program. As part of EIMG adoption (both with the EIMG Instructional Video [phase I] and the EIMG Onboard Training [phase II]), clinicians will be guided to identify and refer patients with low physical activity levels with or without any of the following: overweight/obesity, high blood sugar, high blood pressure, or dyslipidemia. Although the provision of referrals is left to the judgement of each clinician, general guidelines for referring patients will be as follows:

- >150 minutes per week of moderate intensity PA (as determined by the PAVS)
- BMI ≥30kg/m^2
- Impaired fasting glucose
- Prediabetes
- Types 2 diabetes mellitus
- Essential hypertension
- Dyslipidemia (including hyperlipidemia, hypertriglyceridemia, hypercholesteremia)

Once a clinician has deemed that a patient would benefit from participating in EIMG, to complete the referral process they will be asked to:

- i. Complete a Risk Severity Assessment to ensure that participating in an exercise training program will be safe and that it is appropriate for their patients;
- ii. Upload the consent and release of information forms signed by the patient (these forms allow the transfer of a limited amount of HIPAA-protected patient health information to the site coordinator at the community PA facility).

This information is electronically sent to a member of the EIMG Referral Team, who checks for completeness and ensures patient eligibility to participate in the PA program. EIMG Referral Team members will contact referring clinicians if any required information is missing or to clarify any safety concerns.

*The final number of patients referred to the EIMG Referral Team will serve as the ‘numerator’ in our Reach calculations (see 13.2 and 13.3).*

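### Primary referral rate (Reach): referrals are counted under a live, PAVS-prompted inactivity rule and eligible patients from an ICD-10 list, and no step makes the first count a subset of the second

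*Combined protocol and SAP*

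**What the plan says.** **Numerator.** Section 7.3: "The final number of patients referred to the EIMG Referral Team will serve as the" numerator of Reach. These referrals arise during clinic visits. Section 4.2 makes the programme open to patients who are "physically inactive (<150 minutes per week of moderate intensity aerobic activity) and with or without a chronic condition". In Section 4.3 the PAVS identifies such patients and "provides a best practice alert (BPA) through the EHR stating that the patient may qualify for EIMG". Section 7.3 adds that "clinicians will be guided to identify and refer patients with low physical activity levels with or without any of the following"; the list that follows there names four groups, among them excess weight that includes overweight as well as obesity. The same section then qualifies this: "Although the provision of referrals is left to the judgement of each clinician". The Referral Team checks completeness and eligibility (7.3), and the care coordinator reviews the chart (13.3).

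**Denominator.** Section 7.4 and its table build it retrospectively from the EHR: Appendix A inclusion codes minus an ICD-10 exclusion list. On the inclusion side: "These conditions include patients that are physically inactive and/or who have obesity, diabetes, hypertension, or dyslipidemia". Appendix A represents inactivity by four codes (Z71.3, Z71.82, Z72.3, Z91.89). No PAVS value is used.

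**Intended relation.** Section 7.2: "These broader sample of patients that were eligible for an EIMG referral will be considered as the denominator". The table in 7.4 describes the numerator as eligible patients who were referred, and 12.2 makes eligible patients within clinics the observational units. All three imply that the numerator is part of the denominator.

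**The concern.** A proportion needs its numerator drawn from its denominator. Here the live rule is built on measured inactivity, with a condition optional, while the list admits anyone with a coded condition, active or not, and sees inactivity only if someone coded it. Sections 7.3 and 12.2 can also lead two competent analysts to different primary outcomes. Under 7.3 a referral of a patient who is not on the list counts; under 12.2 that patient has no record to count.

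Referral rate is the stated primary outcome (Synopsis, 6.2.1). Its absolute level is what another health system would take from the study. Section 11.0 also plans to compare the patients reached with all eligible patients, and that comparison presumes that the first group sits inside the second.

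**Working it through.** **1. The two rules side by side**

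| Patient | Live rule (4.2, 4.3, 7.3) | ICD-10 list (7.4, Appendix A) | Effect on Reach as written |
|---|---|---|---|
| Inactive on PAVS, listed code | eligible | included | consistent |
| Active on PAVS, hypertension code I10 | does not meet the 4.2 activity criterion; referral only on clinician judgement | included | a missed referral if not referred |
| Inactive, overweight with BMI below 30, no inactivity or counselling code and no other listed code | eligible | absent (BMI codes start at 30.0) | if referred, numerator only |

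The second and third rows are the two routes by which the counts separate.

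**2. Is there a linking step?** For the primary rate, Sections 7.2 to 7.4 and 12.2 do not say that referrals are matched to the list, or what happens to those that do not match. For Secondary Aim 2 the link does exist: 12.5.1 builds episodes from patients with an eligible diagnosis, and equation (2) in 12.5.5 sets the referral indicator to 1 or 0 within them.

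**3. The plan's own figure.** The point does not rest on the power calculation, but the calculation shows what a definitional change would do to it. Inputs (12.3): residual SD 0.01, 8 monthly values per clinic, 10 clinics, significance level 0.05 (taken as two-sided). In a random-intercept model with phase and month, the variance factor for phase is 1/(2 − 8²/42) = 2.1, so SE = 0.01 × √(2.1/10) = 0.00458. If the second phase runs parallel and ends at 0.04, the fitted step is 0.018, the ratio is 0.018/0.00458 = 3.93, and average power is 97.5%. The expected minimum over 100 repeats of 100 simulations, which is the plan's reporting convention, is 92.9% against the stated 92%. Three of six two-sided readings of the profile come within 2 points of 92%. If a constant factor multiplies the rates and the SDs together, the ratio of step to SE, and so the power, does not change.

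**4. Direction.** Let *a* be the active share of the list, *u* the share of referrals off the list, and *v* the share of referrals that are active listed patients. Then

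rate among listed inactive patients = reported rate × (1 − u − v)/(1 − a).

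This exceeds the reported rate if u + v < a and falls below it if u + v > a. The documents give none of the three, so the sign is open.

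**5. Phase contrast.** Take a recorded rate of 1% rising to 3%, the level before and just after the step in 12.3, and count only matched referrals. All values of *u* here are assumptions chosen to show the mechanism.
- *u* = 0.2 in both phases: 0.8% to 2.4%. The ratio stays 3.0 and the step is 1.6 points.
- *u* = 0, then 0.2: the step is 2.4 − 1.0 = 1.4 points, and the ratio is 2.4.
- *u* = 0.3, then 0: the step is 3.0 − 0.7 = 2.3 points.

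A stable off-list share rescales the rate but leaves the relative contrast alone. Only a change between phases distorts it, and the distortion can go either way.

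**The case against.** The other side has good arguments, and several stand.

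- *The plan already links referrals to eligible patients.* True for Aim 2, so it would be wrong to say that the plan has no link anywhere. The gap is confined to the primary rate.
- *The numerator is not raw.* Referrals are checked by the Referral Team and by chart review, and 6.2.1 speaks of complete, accurate referrals. But that check is against programme rules, not against the ICD-10 list, so it does not create the subset.
- *The list does include inactivity, and a code list verified by clinicians and the Advisory Board is a defensible denominator.* Accepted. Onboard training covers conducting the PAVS (8.4), so a PAVS-based denominator could itself move with the intervention. This is why the code list should stay primary.
- *Off-list referrals may be few.* Possibly. Apart from overweight below BMI 30, Appendix A broadly tracks the bulleted guidelines in 7.3, and codes recorded by month 8 may bring some such patients in. The documents give no figure.
- *Dropping off-list referrals is only one way to enforce a subset.* Also fair. Adding them to the denominator does so too, and for a reported 4% gives 0.04/(1 + 0.04u): 3.95% at an assumed u = 0.3, against 0.04 × 0.7 = 2.8% when they are dropped. The numbers depend heavily on the remedy, so they are not evidence of the size of the defect.

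The unfinished exclusion list is not a defect in itself: 7.4 sets a process to complete it before patient data are extracted.

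**Conclusion.** The definitional gap is clear from the text. For the primary rate, numerator and denominator follow different rules, a subset is intended, and nothing enforces it. This affects the absolute rate and the comparison of reached with all eligible patients. It should be fixed, but it does not invalidate the trial.

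A reader might infer more. One inference is that the reported rate is known to be too low, because active patients inflate the denominator, or too high, because of off-list referrals. The documents support neither, since they give no overlap or activity shares. Another is that the powered comparison of video with onboarding is biased. That would need patient mix, coding or the off-list share to change between phases. Such a change is possible, because inactivity and exercise-counselling codes could be generated by EIMG activity, but it is not shown.

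**What to change.** 1. **Match for the primary rate.** Keep the ICD-10 list as the primary denominator. Match referrals to it by patient and clinic, as Aim 2's definition already implies, and count only matched referrals in the primary numerator. Report off-list referrals separately by phase. Add a sensitivity analysis that puts them into both numerator and denominator, noting that this adds uncoded patients only if they were referred.
2. **PAVS-restricted sensitivity analysis.** Repeat the analysis among patients whose EHR PAVS shows inactivity. Report PAVS missingness by phase, because onboarding trains PAVS conduct.
3. **Reconcile the criteria and apply them to both counts.** On age, Section 4.2 says "Patients are eligible to participate in EIMG if they are between the ages of 18-80", 7.2 sets 18 or older, and 13.2 excludes only those under 18. On activity, 4.2 uses below 150 minutes per week, while the first bullet in 7.3 uses above 150. The investigators must settle these.

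The cost is protocol and SAP wording plus one patient-level link between the referral list and the EHR extract. Extraction of PAVS and activity data is already planned (9.3.1, 12.5.3). The rule can be fixed before patient data are extracted, alongside the exclusion list. The downside is that some referrals leave the primary numerator, and PAVS will be missing for some patients.

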## **8.0 STUDY PROCEDURES**

### **8.1 Waves of Enrollment**

All eligible Prisma Health primary care clinics will be invited to adopt EIMG at the same time. Prisma Health primary care clinics will not enter clinics into the study via stepped approach. Within this one wave, three distinct study phases will be conducted.

### **8.2 Phase I – EIMG Adoption**

The first phase of this study will involve inviting all eligible Prisma Health primary care clinics to adopt EIMG through a three-step approach, as described below.

#### **8.2.1 Step One – Department Chair Email**

The department chairs for family and internal medicine at Prisma Health will, on behalf of the research team, send a brief email to all physicians and practice managers at eligible Prisma Health primary care clinics. The email will briefly introduce EIMG, discuss its compatibility, complexity, relative advantage, observability, trialability and how adopting it will benefit their clinic, and provide a link to the EIMG website. If a practice manager responds to this email, they will be invited to schedule a brief introductory meeting (section 8.2.3.) to discuss the process of adopting EIMG. If a physician responds to this email, they will be encouraged to reach out to their practice manager so that they can both be jointly involved in the EIMG adoption process. We decided that the practice manager must be included in the adoption process as they are most likely to disseminate information and materials to the clinic staff and serve as the best point of contact for the research team.

#### **8.2.2 Step Two – Communication with Practice Manager**

Approximately one-week after the department chair email, a study coordinator will send a follow up email to each practice manager to gauge their interest in adopting EIMG. Practice managers that express interest in adopting EIMG will be asked to schedule a brief introductory email (section 8.2.3.). If a practice manager expresses that their clinic is not interested in adopting EIMG, the clinic will be considered as a ‘non-adopter’. If the practice manager does not respond to the email within one week, the study coordinator will attempt to call the practice manager up to three times over the following ten days. If the study coordinator is unable to get in touch with the practice manager, they will be considered unresponsive and their clinic will be classified as a ‘non-adopter’.

#### **8.2.3 Step Three – Brief Introductory Meeting with Practice Managers**

A study coordinator will conduct a brief, 15-minute meeting with practice managers at clinics interested in adopting EIMG. The meeting will be held in-person or virtually at the request and convenience of the practice manager. During the meeting, the study coordinator will provide an overview of the adoption process (phase II and phase III), discuss the EIMG Introductory Video and the timeline for its dissemination and EIMG activation at the clinic, explain the optional research components accompanying EIMG adoption (adoption interview, section 9.1.1; online ORCA questionnaire, section 9.1.2; individual interviews with clinic staff, section 9.1.3), and answer any questions from the practice manager.

### **8.3 Phase II – EIMG Instructional Video**

Phase II will start with disseminating the EIMG Instructional Video to adopting clinics, followed by EIMG activation. The EIMG Instructional Video is intended to be a low-intensity strategy for disseminating information and guidance on EIMG and the PA referral pathway connecting Prisma Health primary care clinics and the community PA facilities. The EIMG Instructional Video is a brief (11-minute), voice-over PowerPoint presentation that provides information on: a) the origins of EIMG, b) the 12-week, community-based PA program, c) initial patient effectiveness results, and d) process for placing an EIMG referral. The EIMG Instructional Video will be sent to the practice managers at EIMG-adopting clinics for broader dissemination to all

clinic staff. After delivery of the EIMG Instructional Video to the practice managers, access to the EIMG referral process in the EHR is *'turned on'* (aka – EIMG activation) allowing clinic staff to electronically identify and engage with eligible patients.

#### **8.4 Phase III – EIMG Onboard Training**

Phase III will consist of a more in-depth standardized EIMG onboard training that will take place with EIMG-adopting Prisma Health primary clinics (section 8.2). The EIMG onboard training will be scheduled in collaboration with the clinic practice manager on a day and time most convenient for the clinic staff. The scheduling of the EIMG onboard training will occur during the second half of month 4, with the trainings taking place during the first half of month 5. The onboarding process will follow an established protocol that has been iteratively developed and refined from lessons learned through the addition of EIMG clinics between 2016-21. Due to the coronavirus pandemic, the onboard training process was adapted for virtual environments and will be used moving forward due to its notable benefits, including recording the training to serve as an ongoing reference tool for clinic staff who cannot attend initial training, as well as new and incoming staff. The standardized, yet flexible and adaptable training is targeted to practice managers, healthcare providers, nurses, and front-office staff at clinics. The training includes a detailed explanation of the EIMG Clinical Education Workflow, a breakdown of responsibilities for each part of the EIMG process (i.e., conducting the PAVS, obtaining the consent and release of information forms), and completing the risk severity assessment. Strategies used in the onboard training will be mapped to implementation strategies compiled as a part of the Expert Recommendations for Implementing Change (ERIC).

## 9.0 STUDY EVALUATION AND ASSESSMENTS

This study is evaluating the adoption and implementation of an existing program (EIMG), which has previously been adopted and is in use by >27 Prisma Health clinics, at Prisma Health primary care clinics that have not yet had the chance to adopt this program. Our study will conduct research activities examining adoption, implementation, and effectiveness across three different groups of individuals:

- Practice managers at Prisma Health primary care clinics that are eligible to adopt EIMG;
- Clinic staff at Prisma Health primary care clinics that adopt EIMG;
- Patients at primary care clinics that adopt EIMG and receive an EIMG referral.

All individuals that agree to participate in research activities will go through an informed consent process as described in section 14.3. A timeline for the following research activities is summarized in section 10.

